9.4 Repeat Hospitalisation due to Heart Failure and Death

To take account of recurrent hospitalisations due to heart failure, while also accounting for the competing mortality, a parametric joint frailty model will be used. The aim is to analyse repeat hospitalisations due to heart failure while accounting for their associated mortality risk. This will be achieved by specifying distributions for recurrent hospitalisations due to heart failure as well as for time to death and including individual-specific latent variables to allow for an association between the two event processes. This would yield a hazard ratio and 95% CI for recurrent hospitalisations due to heart failure (which accounts for mortality as informative censoring) as well as a hazard ratio and 95% CI for all-cause mortality. We will also undertake a negative binomial model to mitigate any potential issues in the development with the above model.⁷⁻⁹

9.5 Win Ratio for Death, Repeat Hospitalisation due to Heart Failure and KCCQ

The win ratio method will be used to account for the hierarchy of events as well as to incorporate repeat hospitalisations due to heart failure. The win ratio is the ratio of "winners" on PCI compared to "losers" thus a value above 1 indicated a benefit of PCI. Confidence intervals will be calculated as well as p-values and will incorporate all-cause mortality, hospitalisation due to heart failure and KCCQ at two year. The outcome hierarchy is as follows:

- (1) Time to all-cause death
- (2) Number of hospitalisations due to heart failure
- (3) KCCQ score at 2 years

The win ratio will use an unmatched pairs approach with each individual in the PCI arm compared to each individual in the OMT arm, using the stepwise sequence above, to adjudicate a winner/loser or declare a tie. If the comparison comes down to the KCCQ score at 2 years and this metric is not available for at least one of the patients REVIVED SAP

then a tie will be declared. For each comparison the common follow-up interval will be defined, i.e. follow-up will be censored, at the duration of the shorter follow-up interval of the relevant pair.

9.6 Other Planned Analyses

9.6.1 Impact of COVID-19

The last patient was randomised on 19th March 2020, four days before the first UK-wide lockdown was announced on 23rd March 2020 due to COVID-19. To allow for potential increase in event rates due to the COVID-19 pandemic and the potential impact on follow-up in REVIVED (e.g. increased delay to PCI and challenges in follow-up) additional analyses will be undertaken.

The event rates for all-cause death and hospitalisation due to heart failure will be compared pre- and post- 23rd March 2020 when the lockdown was announced. These analyses will account for time since randomisation. Rates will be compared in follow-up periods since randomisation with cut-points chosen based on the number of events available across follow-up in the pooled treatment groups before the treatment code is broken (e.g. 0-6 months, 6 months to 1 year then beyond 1 year).

An analysis will be undertaken of the primary outcome and component events comparing the impact of the interventions pre- and post- 23rd March 2020. The treatment effect together with 95% confidence intervals will presented by these time periods and formally assessed with an interaction test between time period and treatment from the Cox model.

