Several considerations should be taken into account when interpreting the above data. Firstly, although the trial at its onset mandated the presence of viability for enrolment, due to slow recruitment this was removed from the protocol; as a result, a patient population with both non-viable and viable myocardium were enrolled. Secondly, on average 2 patients were enrolled per centre per year, reflecting the fact that this was a difficult trial to recruit to, and may indicate selection bias. Importantly, the CABG procedure itself conferred a higher 30-day mortality than with medical therapy, which may have ameliorated any benefit seen with revascularisation, an effect which lasted for more than 2 years. This finding is in keeping with registry data on CABG surgery: perioperative mortality rates in patients with LV dysfunction have been shown to be between 5% and 30%; and the risk increasing with age, comorbidities and degree of LV impairment(21). The relative risk of early death following CABG surgery in patients with severe LV dysfunction is 3- to 4-fold higher than in those with mild dysfunction or preserved systolic function(22-24). However for patients who survive this early mortality hazard, there may be a long-term mortality benefit from CABG. Another consideration is the age of the population enrolled in STICH(ES) and whether this relatively young population are representative of the average heart failure patient. In STICHES, the reduction in mortality was about 25% for those aged <60 years (slightly more than half of all patients) but only 9% in those aged >60 years.

Furthermore, patients with left main coronary stenoses (who represent the extreme end of the spectrum of coronary disease and therefore are at highest risk of cardiovascular events) were excluded from the trial. Finally, the STICH investigators did not systematically exclude patients with non-ischaemic cardiomyopathy with co-existent coronary disease; a minimum coronary disease severity was not mandated and, as a consequence, 40% of the entire cohort had single or 2 vessel disease only. Potential inclusion of non-ischaemic cardiomyopathy patients would be expected to dilute any beneficial effects of revascularisation.

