9 EVALUATION OF EFFICACY PARAMETERS

9.1 Analysis of Primary Outcome Variable: All-cause Death or Hospitalisation due to Heart Failure

The primary analysis will be a comparison of the incidence of all-cause death or hospitalisation due to heart failure over all available follow-up between the intervention (treatment with PCI) and control (OMT alone) arms of the trial. An REVIVED SAP

unadjusted time-to-event analysis will be performed on the primary endpoint, with the time to the first event (or censoring) measured from randomisation on an ITT basis. Hazard ratios together with associated confidence intervals will be calculated from the Cox proportional hazards model. A p-value for the treatment difference will be calculated using a likelihood ratio test. The proportionality assumption underlying the Cox model will be assessed via Nelson-Aalen plots by treatment group and by a more formal test comparing treatment hazard ratios across appropriate pre-specified follow-up time bands. If there is clear non-proportionality, comparisons will also be made in early and later follow-up using cut-points at 6 months, 1 year, and 2 years. Cumulative event rates will be calculated and presented using Kaplan-Meier time-to-event curves. As a measure of absolute treatment difference, cumulative event rates based on Kaplan-Meier estimates will be compared at 2 years and a 95% confidence interval for the difference calculated. Losses to follow-up are expected to be minimal and patients will be included up until the time they experience the event or are censored.

A secondary sensitivity analysis will be performed for the primary endpoint using a Cox model adjusted for those risk factors identified in the risk score model developed for subgroup analysis (Section 6.5.5).

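### The COVID-19 treatment-by-period test in SAP 9.6.1 does not separate calendar period from time since randomisation, so a changing PCI hazard ratio could be misread as a pandemic effect

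*Protocol*

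**What the plan says.** SAP 9.6.1 plans two analyses around the lockdown date.

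- **Pooled event rates** before and after 23 March 2020. For these the section says "These analyses will account for time since randomisation" and describes comparing rates within follow-up periods.
- **Treatment effect**, in a separate paragraph: an analysis of the primary outcome and its components "comparing the impact of the interventions pre- and post- 23rd March 2020", with period-specific estimates, "formally assessed with an interaction test between time period and treatment from the Cox model". No term for treatment by time since randomisation is named.

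The same section states: "The last patient was randomised on 19th March 2020, four days before the first UK-wide lockdown was announced".

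Two statements in SAP 9.1 bear on this. The time-to-event analysis runs "with the time to the first event (or censoring) measured from randomisation on an ITT basis". Separately, if proportionality clearly fails, "comparisons will also be made in early and later follow-up using cut-points at 6 months, 1 year, and 2 years". Section 9.6.1 does not refer to that assessment.

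**The concern.** Because nobody was randomised after the cut, each patient's post-lockdown time is later follow-up than that patient's own pre-lockdown time. Across the trial, early follow-up lies almost wholly before the cut.

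Running the Cox clock from randomisation removes differences in the baseline hazard between early and late follow-up. It does not remove a difference in the hazard ratio between early and late follow-up. With only a period-by-treatment term in the model, that term absorbs any such difference.

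The analysis is there to say whether the pandemic altered the treatment effect. As written, a positive interaction has two candidate explanations, and the model contains nothing to separate them. A real late benefit of PCI could be discounted as a product of the pandemic, or a pandemic effect could be claimed where there was none.

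**Working it through.** **Inputs from the documents.** Recruitment from 1 September 2013 (SAP Appendix 2) to 19 March 2020 (SAP 9.6.1); cut on 23 March 2020; follow-up to 31 March 2022 (SAP Appendix 2). SAP 4.2 gives 700 patients 1:1, 36% OMT risk at 2 years, HR 0.7, 300 events, 5% significance, up to 5% losses and increasing recruitment. The documents give no early and late hazard ratios for PCI, so those below are assumptions.

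**The plan's own figures.** The plan states no operating characteristic for the COVID-19 test, so the sample-size figures are checked as the base.

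- Schoenfeld power: z = (√300 / 2) × |ln 0.7| = 8.660 × 0.3567 = 3.089; 3.089 − 1.960 = 1.129; power = Φ(1.129) = 87.1%. The stated figure of over 85% is reproduced.
- PCI risk at 2 years: 1 − 0.64^0.7 = 26.8%, the stated 27%.
- OMT hazard: −ln(0.64)/2 = 0.223 per year.

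**How far period and follow-up time overlap.** Share of person-time in each follow-up band, from the simulation below:

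| Band | Increasing recruitment: pre / post | Uniform recruitment: pre / post |
|---|---|---|
| 0-6 months | 27.9% / 3.1% | 21.2% / 1.9% |
| 6-12 months | 20.7% / 8.1% | 17.1% / 5.2% |
| 1-2 years | 27.0% / 25.8% | 25.5% / 17.4% |
| Over 2 years | 24.4% / 63.0% | 36.2% / 75.5% |

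**The mechanism by hand.** Each period's hazard ratio is roughly the event-weighted geometric mean of the band hazard ratios. With increasing recruitment, about 84.5 of 240.5 pre-lockdown events (35.1%) and 6.4 of 139.6 post-lockdown events (4.6%) fall in months 0-6. These shares come from the 1.5 / 1.0 / 0.8 / 0.6 pattern and serve here as an approximation. Take HR 1.5 for six months, then 0.7:

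- Pre: 0.351 × ln 1.5 + 0.649 × ln 0.7 = 0.142 − 0.231 = −0.089, so HR ≈ 0.91.
- Post: 0.046 × ln 1.5 + 0.954 × ln 0.7 = 0.019 − 0.340 = −0.322, so HR ≈ 0.72.
- Ratio post/pre ≈ 0.79, with no pandemic effect present.

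**Simulation.** 1,000 trials per scenario with no pandemic effect. The Cox model used time since randomisation, with treatment, time-updated period and their interaction, and a Wald test at two-sided 5%. It was then refitted with treatment by follow-up band added. The OMT hazard is constant at 0.223 per year, and results are shown as increasing / uniform recruitment.

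| Assumed PCI hazard ratio | Ratio post/pre | Rejection as planned | Rejection with bands added |
|---|---|---|---|
| 0.7 throughout | 1.00 / 1.00 | 5.2% / 6.9% | 5.3% / 7.1% |
| 1.5 to 6 months, then 0.7 | 0.79 / 0.82 | 19.5% / 15.4% | 5.6% / 6.3% |
| 1.5, 1.0, then 0.6 after 1 year | 0.71 / 0.74 | 35.4% / 27.4% | 5.6% / 6.1% |
| 1.5, 1.0, 0.8, 0.6 | 0.72 / 0.74 | 33.0% / 28.6% | 6.0% / 6.2% |
| 2.0, 1.0, then 0.5 (extreme) | 0.57 / 0.61 | 71.7% / 56.4% | 5.8% / 6.4% |

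The simulation standard error at 5% is √(0.05 × 0.95 / 1000) = 0.7 percentage points. With the bands added, the mean ratio is 0.996-1.005 in every scenario.

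**Calibration to the planned events.** A constant hazard to March 2022 gives about 360-430 events, above the planned 300. Keeping 36% at two years and lowering the later hazard (how it falls is an assumption) gives roughly 270-340 events. Rejection is then:

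- 13-22% for HR 1.3 in year 1, then 0.7
- 29-38% for HR 1.5 in year 1, then 0.6
- 7-12% for HR 1.3 for six months, then 0.7
- about 3-6% for a constant HR of 0.7

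**The case against.** The strongest reply is that the documents do not predict an early-harm, late-benefit course for PCI.

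- The early hazard in Protocol 2.3, "an effect which lasted for more than 2 years", belongs to CABG. SAP section 2 contrasts surgery's early hazard with a possibly better balance for PCI, and Protocol 2.4 reports 1.3% one-month mortality after PCI.
- The trial is sized on a single hazard ratio of 0.7, under which the test is sound.
- The 9.1 cut-points are a contingency and not a forecast.

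All of this stands. It limits how likely the problem is, but does not remove it. A changing effect remains plausible for reasons specific to this trial: Protocol section 12 sets no time limit to PCI, and Protocol 4.4 counts heart failure that prolongs the assigned PCI admission as an endpoint event.

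A second reply is that SAP 9.1 already examines proportionality with plots, a formal test and banded estimates, which readers would have beside the COVID-19 result. That is fair, and it means the two explanations are not wholly beyond reach. But 9.6.1 does not link to it, and two separate positive tests would come with no stated way to apportion them.

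A third reply is that the sentence on accounting for time since randomisation covers the interaction too. It sits in the event-rate paragraph and is explained there by rate bands. Even read generously, it does not name the term needed.

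A reader might infer that the trial would report an ordinary PCI course as a pandemic effect. That is too strong: under the moderate patterns most trials would show no significant interaction. What is systematic under non-proportional hazards is the shift in the estimated ratio.

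**Conclusion.** The point holds as a weakness of one supportive analysis. The planned interaction test is valid if the PCI hazard ratio is constant (rejection about 5-7%). If the hazard ratio moves from harm to benefit over follow-up, the test attributes part of that movement to the pandemic. Under the moderate patterns tried, it rejects in roughly 7-38% of trials with no pandemic effect.

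That range rests on assumed early and late hazard ratios, on the recruitment shape and on the event count. The extreme pattern goes higher and should not be taken as typical.

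The documents do not support reading this as a threat to the trial's main conclusion. The primary estimate in SAP 9.1 does not use the period split, and no decision rule in the SAP depends on the COVID-19 interaction.

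**What to change.** In SAP 9.6.1, state that the period-by-treatment interaction will be fitted with period as a time-updated covariate, in a Cox model that also contains treatment by time since randomisation. Use the 9.1 cut-points (6 months, 1 year, 2 years), merging the early bands if events are sparse. Add that the result will be interpreted alongside the 9.1 proportionality assessment.

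Do not report separate post-lockdown hazard ratios within the early bands. Recruitment stopped four days before the cut, so only about 2-6 post-lockdown events are expected in months 0-6 and about 6-17 in months 6-12, both arms together.

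The cost is a sentence or two and a few model terms (three with the full set of bands), with some loss of precision. The SD of the log ratio rises from about 0.22-0.24 to 0.25-0.27. At 0.22 the 95% limits are the estimate multiplied and divided by exp(1.96 × 0.22) = 1.54; at 0.25 the factor is exp(1.96 × 0.25) = 1.63. The adjustment in the early bands will rest mainly on pre-lockdown data, and the report should say so.

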9.6.2 Implantation of Devices during Follow-up

Date of implantation of ICD or CRT devices after randomisation is collected up to 2 years follow-up. Time to implantation will be compared between treatment groups using the same methods as described for the primary outcome (Section 9.1).

9.6.3 Echocardiography Data Core Laboratory

More detailed exploratory analyses will be performed on echocardiography data sent to the core laboratory at baseline, 6 months and 1 year post randomisation. In addition to LVEF analyses further exploratory analyses on other echocardiographic parameters will also be undertaken.

9.6.4 Acute Myocardial Infarction

For the primary analysis, myocardial infarction will be defined according to the third universal definition of myocardial infarction (UDMI).¹¹ In order to account for variable definitions of myocardial infarction, secondary sensitivity analyses may be performed with MI defined according to the 4th UDMI and the Society for Cardiovascular Angiology and Interventions (SCAI) definition of periprocedural MI.^{12,13}

10 EVALUATION OF SAFETY PARAMETERS

10.1 Adverse Events

Adverse events (AE) and serious adverse events (SAE) will be reported as the proportion of patients in each treatment group that suffer an event. These outcomes will be reported using the ITT.

11 ANALYSIS OF HEALTH ECONOMIC OUTCOMES

11.1 General

The REVIVED-BCIS2 protocol specifies that a within-trial analysis (WTA) - an analysis using trial data only – will be undertaken to assess the costs and effects of OMT and PCI in study participants. Although WTA is considered to have high internal validity, there is a growing awareness that the findings from any RCT should not be considered in isolation but, in fact, are more valuable from a decision-making context when used in a broader context together with additional evidence. Thus, in addition to conducting the trial-level analysis, a REVIVED-BCIS2 economic analysis will be conducted to extend from the single trial to look at long-term costs and outcomes, using all relevant evidence and available interventions. REVIVED-BCIS2 will thus provide a means of collecting data to support a cost-effectiveness analysis of PCI in heart failure. This extended analysis will incorporate the findings from REVIVED-BCIS2 trial into the wider existing evidence base including other evidence any alternative treatments. Such an analysis requires the development of a decision analytic model to accommodate multiple different information sources and will be detailed in a separate analysis plan.

11.2 Within-trial Analysis Outline

The within-trial economic analysis will be performed using individual patient-level data from the REVIVED-BCIS2 trial. Health resource consumption and costs within the trial will be estimated. The outcome measure will be the EQ-5D index score, via the generic preference-based instrument EQ-5D-5L. The economic analysis will be conducted using the perspective of UK NHS and the Personal Social. The period of analysis is 8 years which is the maximum period of patient follow-up in the trial. Following standard convention in economic evaluation, future costs and health outcomes will be discounted. The analyses will be conducted using appropriate statistical software such as R version 4.1.1 or Stata® version 17.1 or later.

11.1 Analysis Methods

11.1.1 Health Resource Consumption and Costs

Data on resource use will be collected for the entire duration of the trial for each participant. Costs will be calculated for each trial participant as the product of resource units used and the relevant unit cost.

The following types of resource use will be used for cost estimation: Cost of treatments undertaken (trial or non-trial treatments, e.g. IV diuretics). Costs of out-patient hospital visits and hospital in-patient stay Costs of events since discharge e.g. unplanned revascularisation Costs of cardiac medication e.g. statins Resource use information will be available from study data record forms (CRFs) for each patient. For each participant the relevant resource use information will include: Number of hospital admissions without overnight stays due to HF or other reasons Number of nights in hospital for in-patient stay due to HF or other reasons The type and number of trial treatments The type and number of non-trial treatments, including medication The year of pricing will be of 2021. Unit costs associated with resource use in each treatment arm will be estimated based on the appropriate version of NHS reference costs database and Personal and Social Services Research database. Unit costs of REVIVED SAP

treatment products will be obtained from the appropriate edition of British National Formulary (BNF). In case the information is not available in the BNF database, product costs will be obtained from the manufacturer.

The results section will summarise the costs by type of resource consumed for the two treatment arms. Descriptive statistics for total costs will also be summarised by trial arm at baseline, 6 months, yearly and end of trial follow-up.

11.1.2 Health Benefits

Health benefits will be considered as the change in individual level health-related quality of life (HRQoL) as measured in terms of 'utility' estimates over the study period. Changes in patient utility level will be measured using EQ-5D-5L questionnaire that evaluates patient's HRQoL on the following five dimensions: mobility, self-care, usual activities, pain/discomfort and anxiety/depression. EQ-5D-5L questionnaire was administered at baseline and also at 6 months, yearly and at the end of trial follow-up period to assess utility level at each time point. A value set for the EQ-5D-5L is now available that reflects the preference of members of the public in England for health states that are defined by the EQ-5D-5L descriptive system. However, a new value set is currently under development. NICE current recommendation on the use of the EQ-5D advises that utilities for the 5L are derived using the mapping function developed by NICE DSU, namely the EQG and the NDB methods (i.e. mapping of the 5L descriptive system data onto the 3L valuation set). Therefore, unless the NICE guidance is changed by the time of our analysis, the mapping will be used to derive utilities for the participants in the REVIVED-BCIS2 trial.

All EQ-5D-5L data will be rechecked to ensure that all scores are within the expected parameter space. As for resource use and costs, EQ-5D index scores will be calculated for each patient over the follow-up period and assessed in its distribution. The results section will summarise the EQ-5D index scores by treatment arm at baseline, 6 months, yearly and end of trial follow-up.

11.1.3 Missing Data

Missing data (for reasons other than censoring) will be evaluated to assess the occurrence of specific patterns. If needed, missing data will be handled through the most adequate methodology in line with the overall statistical analysis plan of REVIVED-BCIS2 study.

11.1.4 Sensitivity Analysis

Sensitivity analysis will be considered in line with the statistical analysis plan. Further sensitivity analysis will also be considered, including investigating the impact of assumptions around resource use and unit costs.

11.2The Economic Analysis Data Validation

The within-trial economic analysis will use the validated dataset produced for the statistical analysis of the RCT. Data on health services resource use and HRQoL (EQ-5D) will be separately validated for the economic analysis. Further validation of the data will be undertaken as follows:

[figure not shown]
_	Participants for whom there are no cost and outcome data other than baseline
will be	considered as censored a day after randomisation.
	Data will be assessed and any queries relating to resource use and quality of
ife wil	l be communicated to the trial team for clarification. Decisions regarding raised
data q	ueries will be made in conjunction with the trial team and clearly documented.

